11 DEVIATIONS FROM THE CIP

The investigator is not allowed to deviate from the CIP except under emergency circumstances to protect the rights, safety and well-being of the subjects. Such deviation shall be documented and reported to the Sponsor and the EC as required.

The procedure for recording and reporting CIP deviations shall be via a CIP Deviation CRF in the EDC system. Analysis of CIP deviations shall be undertaken by the Sponsor and Data Management.

In the event of a CIP deviation, the investigator shall notify the Sponsor within the required notification window. The Sponsor shall notify the EC and competent authority where necessary, of all CIP deviations annually.

12 DEVICE ACCOUNTABILITY

Investigational devices shall be tracked and returned to the Sponsor upon completion of the study.

13 STATEMENTS OF COMPLIANCE

13.1 Declaration of Helsinki and compliance with standards

The clinical investigation shall be conducted in accordance with the ethical principles that have their origin in the Declaration of Helsinki (2013), the ISO 14155:2011 Standard, and any regional or national regulations, as appropriate.

13.2 Ethics Committee and Regulatory Agency Approval

The clinical investigation shall not commence in a particular region prior to the written favorable opinion or approval from the local Ethics Committee (EC), and regional regulatory agency (i.e., Competent Authority, Food and Drug Administration, or other relevant agency) is obtained.

The Principal Investigator shall submit the final approved version of the CIP, the approved PIC and all subsequently approved documents to the EC and regulatory agency (RA) where applicable. A copy of the EC and RA opinion/approval shall be provided to the Sponsor if not directly communicated.

The investigator shall forward any amendment made to the approved PIC any other written information to be provided to the subject for review and approval by the Sponsor prior to submission to the EC.

The Sponsor and Principal Investigator shall continue the communication with the RA and EC as required by national regulations, the clinical investigational plan or the responsible RA and EC.

Any additional requirements imposed by the EC or RA shall be followed.

The investigator shall submit the appropriate documentation if any extension or renewal of the EC or RA approval is required. In particular, substantial amendments to the CIP, the PIC, or other written information provided to subjects shall be approved in writing by the EC and RA.

The investigator will report to the RA and EC any new information that may affect the safety of the subjects or the conduct of the clinical investigation. The investigator/sponsor shall send written status summaries of the investigation to the RA and EC regularly as per local RA and EC requirements.

Upon completion of the clinical investigation, the investigator/sponsor shall provide the RA and EC with a brief report of the outcome of the clinical investigation as per local RA and EC requirements.

The clinical investigation is covered by a clinical trial insurance meeting the requirements of the participating countries.

14 INFORMED CONSENT PROCESS

14.1 Obtaining informed consent

The investigator shall obtain written informed consent using an approved Patient Informed Consent Form (PIC) from the subject prior to any clinical investigation related examination or activity. The rationale for and the details, aims and objectives of the investigation, the risks and benefits and alternative treatments, and the extent of the subject's involvement shall be explained. Ample time shall be provided for the subject to inquire about details of the clinical investigation and to decide whether to participate. All questions about the clinical investigation shall be answered to the satisfaction of the subject or the subject's legally acceptable representative. Subjects shall not be coerced or unduly influenced to participate or to continue to participate in a clinical investigation.

A copy of the signed PIC shall be given to the subject. The original signed PIC shall be archived in the Investigator's File at the investigational site, according to the requirements of the country's health regulations

The subject or the subject's legally acceptable representative shall be informed in a timely manner if new information becomes available that may be relevant to the subject's willingness to continue participation in the clinical investigation. The communication of this information shall be documented.

14.2 Data Privacy

Subjects will be identified on CRFs or similar documents (for example, questionnaires) by a unique subject identification code. Completed CRFs or similar documents are confidential documents and will only be available to the Sponsor and their representatives, the investigator, the investigational statistician, and if requested to the Ethics Committee and national regulatory authorities.

The investigator and site staff will not include the name of any subject in any CRF or other forms, electronic files, imaging items (for example, x-ray), publication, or submission to a regulatory authority; will not otherwise disclose the identity of any subject; and, in any CRF, will refer to each subject by their identification code. The Patient ID log CRF is explicitly excluded from this requirement.

15 REPORTING PROCESS FOR ADVERSE EVENTS, ADVERSE DEVICE EFFECTS AND DEVICE DEFICIENCIES

15.1 Definitions

All definitions are according to 21 CFR Part 812, 50, 54, 56 & 11 as well as the EN ISO 14155:2011 standard.

15.1.1 Adverse event (AE)

Any untoward medical occurrence, unintended disease or injury, or untoward clinical signs (including abnormal laboratory findings) in subjects, users or other persons whether or not related to the investigational medical device.

NOTE 1: This definition includes events related to the investigational medical device or the comparator.

NOTE 2: This definition includes events related to the procedures involved.

NOTE 3: For users and other persons, this definition is restricted to events related to investigational medical devices.

15.1.2 Adverse device effect (ADE)

Adverse device effect is an adverse event related to the use of an investigational medical device.

NOTE 1: This includes any adverse event resulting from insufficiencies or inadequacies in the instructions for use, the deployment, the implantation, the installation, the operation, or any malfunction of the investigational medical device.

NOTE 2: This definition includes any event resulting from use error or from intentional misuse of the investigational medical device.

15.1.3 Device deficiency (DD)

A device deficiency is an inadequacy of a medical device with respect to its identity, quality, durability, reliability, safety or performance.

NOTE: Device deficiencies include malfunctions, use errors, and inadequate labelling.

15.1.4 Serious adverse event (SAE)

A serious adverse event is any adverse event that:

- 1) led to a death,
- 2) led to a serious deterioration in the health of the subject that either resulted in
 - a) a life-threatening illness or injury, or
 - b) a permanent impairment of a body structure or a body function, or
 - c) in-patient hospitalization or prolonged hospitalization, or
 - d) medical or surgical intervention to prevent life-threatening illness or injury or permanent impairment to a body structure or a body function,
- 3) led to fetal distress, fetal death or a congenital abnormality or birth defect

NOTE. Planned hospitalization for a pre-existing condition, or a procedure required by the CIP, without serious deterioration in health, is not considered a serious adverse event.

15.1.5 Serious adverse device effect (SADE)

A serious adverse device effect is an adverse device effect that has resulted in any of the consequences characteristic of a serious adverse event.

15.1.6 Unanticipated serious adverse device effect (USADE)

An unanticipated serious adverse device effect is a serious adverse device effect which by its nature, incidence, severity or outcome has not been identified in the risk analysis report (for the investigational device or its comparator).

15.2 Reporting process for adverse events, adverse device effects and device deficiencies

The investigator shall report all serious adverse events without delay to the Sponsor. Investigators are to inform their respective EC/IRBs and the Sponsor immediately if an unanticipated adverse device effect is suspected (no more than 10 working days after the investigator learns of the effect). If the case is determined to be an unanticipated adverse device effect, the investigator will fill out an "Unanticipated Adverse Device Effect Form". The Sponsor will report the results of an evaluation of the unanticipated adverse device effect to all reviewing ECs and investigators within 10 working days after first receiving notice of the event.

The details of the Medical Monitor for the clinical investigation are:

Name of Medical Monitor	[name]
Phone number (business hours)	[name]
Phone number (after hours)	[name]
E-mail	[contact]

If applicable: The Sponsor is responsible to report all SAEs, SADEs and USADEs to the relevant RAs in the clinical investigation in accordance with local regulations.

The investigator has to report all AEs, SAEs, SADEs and USADEs to their EC and / or RA (if applicable) using the applicable report form and reporting timelines as per national requirement.

Subjects shall be carefully monitored during the clinical investigation for potential adverse events and shall be routinely questioned about adverse events at investigation visits. For all adverse events, information obtained by the investigator shall be recorded in the Adverse Event CRF. The investigator shall attempt to assess the relationship between the investigational device and the adverse event.

15.3 Data Monitoring Committee

Since routine surgical procedures will be applied, a DMC will not be established.

15.4 Device Deficiency Reporting Requirements

The investigator shall report any device deficiency without unjustifiable delay to the Sponsor.

Name of Medical Monitor	[name]
Phone number (business hours)	[name]
Phone number (after hours)	[name]
E-mail	[contact]

16 INCIDENT REPORTING

Not applicable for this clinical investigation.

17 VULNERABLE POPULATION

Not applicable for this clinical investigation.

18 SUSPENSION OR PREMATURE TERMINATION

The Sponsor will withdraw from sponsorship of the clinical investigation if:

- 1) major non-adherence to the CIP is occurring
- 2) it is anticipated that the subject recruitment will not be adequate to meet the objectives of the clinical investigation

Should the Sponsor withdraw from sponsorship of the clinical investigation, the Sponsor will continue sponsorship for the subjects already recruited into the investigation.

An ongoing clinical investigation can be discontinued in case of:

- 1) device failure
- 2) serious or intolerable adverse device effect, leading to the explant or discontinued use of the device
- 3) subject's death
- 4) investigator's decision
- 5) subject's decision

19 PUBLICATION POLICY

A description of this clinical investigation will be available on <http://www.ClinicalTrials.gov>, as required by U.S. Law.

It is planned to generate a joint publication by the Principal Investigator(s) and the Sponsor. The responsibility for writing the publication is with the Coordinating Investigator or the Sponsor. Authorship will be based on contribution of complete datasets and contribution to paper preparation according to the rules of the journal chosen for publication. The joint publication shall be reviewed by the Sponsor at least 30 days in advance to any release of publication. If the publication contains information that the Sponsor at his discretion finds worth protecting in the form of a patent or trademark etc., the Sponsor has the right to delay the publication or presentation for 90 days.

Following acceptance of the joint paper, the investigators will be able to publish as they wish. The publishing investigator will provide the Sponsor with a manuscript copy of the abstract and paper at least 30 days in advance of publication or presentation. If the publication contains information that the Sponsor at his discretion finds worth protecting in the form of a patent or trademark etc., the Sponsor has the right to withhold the publication or presentation for 90 days.

21 CHANGE HISTORY

List the details of the changes made since the previous approval.

Version	Change	Author	Date
1.0	IDE Submission	[name] & [name]	19 December, 2016
2.0	Amendments requested from FDA	[name] & [name]	9 March, 2017
3.0	Clarification re FUV1 and FUV2 windows added	[name]	23 August, 2017

22 DEFINITIONS

22.1 Definitions from ISO 14155:2011

Term	Description
Adverse event (AE)	
Any untoward medical occurrence, unintended disease or injury, or untoward clinical signs (including abnormal laboratory findings) in subjects, users or other persons whether or not related to the investigational medical device.
 
NOTE 1: This definition includes events related to the investigational medical device or the comparator
 
NOTE 2: This definition includes events related to the procedures involved.
 
NOTE 3: For users and other persons, this definition is restricted to events related to investigational medical devices.

Adverse device effect (ADE)	
Adverse device effect is an adverse event related to the use of an investigational medical device.
 
NOTE 1: This includes any adverse event resulting from insufficiencies or inadequacies in the instructions for use, the deployment, the implantation, the installation, the operation, or any malfunction of the investigational medical device.
 
NOTE 2: This definition includes any event resulting from use error or from intentional misuse of the investigational medical device.

Device deficiency (DD)	
A device deficiency is an inadequacy of a medical device with respect to its identity, quality, durability, reliability, safety or performance.
 
NOTE: Device deficiencies include malfunctions, use errors, and inadequate labelling.

Incident	
Any malfunction or deterioration in the characteristics and/or performance of a device, as well as any inadequacy in the labelling or the instructions for use which, directly or indirectly, might lead to or might have led to the death of a subject, or USER or of other persons or to a serious deterioration in their state of health.

Serious adverse event (SAE)	
A serious adverse event is any adverse event that:
 
 a) led to a death, b) led to a serious deterioration in the health of the subject that either resulted in 
 1) a life-threatening illness or injury, or 2) a permanent impairment of a body structure or a body function, or 3) in-patient hospitalization or prolonged hospitalization, or 4) medical or surgical intervention to prevent life-threatening illness or injury or permanent impairment to a body structure or a body function, c) led to fetal distress, fetal death or a congenital abnormality or birth defect 
NOTE Planned hospitalization for a pre-existing condition, or a procedure required by the CIP, without serious deterioration in health, is not considered a serious adverse event.

Term	Description
Serious adverse device effect (SADE)	A serious adverse device effect is an adverse device effect that has resulted in any of the consequences characteristic of a serious adverse event.
Unanticipated serious adverse device effect (USADE)	An unanticipated serious adverse device effect is a serious adverse device effect which by its nature, incidence, severity or outcome has not been identified in the risk analysis report (for the investigational device or its comparator).

22.2 Other definitions

Term	Description
CA	Competent Authority
CER	Clinical Evaluation Report
EC	Ethics Committee, alternatively referred to as Institutional Review Board in the U.S.
RA	Regulatory Agency
IB	Investigator's brochure is a compilation of the current clinical and non-clinical information on the investigational device(s) relevant to the clinical investigation.
NCA	National Competent Authority
PASS	Post-authorization safety studies mandated by medical device regulators
PIC	Patient Informed Consent
PICF	Patient Informed Consent Form
PIL	Principal Investigator List
SAP	Statistical Analysis Plan
CRT	Cochlear Response Telemetry
CM	Cochlear Microphonic
SRT	Speech Reception Threshold
DMC	Data Monitoring Committee
AUSTIN	Australian Speech Test in Noise
CRF	Case Report Form
EC	Ethics Committee
ECoG	Electrocochleography
POV	Pre-operative Visit
FUV	Follow-Up Visit

23 APPENDIX A: INSTRUCTIONS FOR MASKING

- a) Pure tone threshold is established in the test ear
- b) Masking noise is introduced to the non-test ear at the initial masking level (10 dB above the established threshold in the non-test ear). Pure tone threshold is then re-established.
- c) Level of the masking tone or noise is increased subsequently by 5 dB. If there is a response to the tone in the presence of the noise, the level of the noise is increased by 5 dB. If there is no response to the tone in the presence of the noise, the level of the tone is increased by 5 dB steps until a response is obtained.
- d) A plateau has been reached when the level of the noise can be increased over a range of 15 to 20 dB without shifting the threshold of the tone. This corresponds to a response to the tone at the same HL when the masker is increased in three to four consecutive levels.
- e) Masked pure tone threshold corresponds to the HL of the tone at which a masking plateau has been established.

## 1 INTRODUCTION

This document is a companion document to the Clinical Investigation Plan (D1041816). It includes a comprehensive description of the sample size estimation, the intended statistical analyses with reference to the primary and secondary hypotheses, and additional statistical considerations such as the intended treatment of missing data.

Any deviation from the Statistical Analysis Plan will be reported in the Clinical Investigation Report.

## 2 STUDY POPULATION

The Cochlear Response Telemetry (CRT) system for monitoring the cochlear microphonic (CM) response to acoustic clicks or short tone bursts will be assessed in a clinical population aged 18 years and older, who have received a commercially available Nucleus® CI522, CI532, or Hybrid-L24 cochlear implant.

## 3 STATISTICS

### 3.1 Sample Size

Prospective sample size estimation for a two-sample t-test has been conducted, given that the study uses a between-groups design to investigate its primary hypothesis. Specifically, the planned sample size would provide 80% power at the one-tailed 0.05 alpha level to detect at least 15 dB greater deterioration in low frequency acoustic hearing threshold for subjects with compromised CM compared to preserved CM.

The following general assumptions have been made:

- A difference in mean hearing preservation of 15 dB for the compromised CM versus preserved CM groups. This difference is considered clinically meaningful, based on clinical consensus.
- An expected standard deviation of 25 dB HL. It is more conservative, but is based on the SD of 22.26 dB HL observed in low frequency hearing preservation at 3 months post-operative in the US multi-site clinical trial with 52 cochlear implant recipients using the CI422 straight electrode array (IDE G120234). This trial is considered relevant since the majority of subjects in the prospective trial will be similarly implanted with the Slim Straight array (CI522). Furthermore, in the calculation of the SD for this previous trial, low frequency hearing preservation has been calculated in the same manner as it will be in the prospective study (as the average change in threshold (post-activation minus pre-operative) across the frequencies 500 Hz, 750 Hz and 1000 Hz where there is preoperative hearing  $\leq 80$  dB HL in the implanted ear).
- One-sided 0.05 alpha level, given that the primary endpoint is based on a directional hypothesis.
- A desired power of 0.8.

---

Based on the above assumptions, a minimum sample size of 36 subjects with preserved and 36 subjects with compromised CMs is required to reject a false null hypotheses of equivalent or worse hearing preservation for those subjects with preserved CM (using SigmaPlot 13.0).

This minimum sample size will be increased for the following reasons.

- a. The sample size will be increased by 15% to 41 subjects per group to allow for the possibility that the hearing threshold data is non-normally distributed and that a nonparametric statistical analysis will be required. This 15% increase is based on what is known as the minimum asymptotic relative efficiency (ARE) of the Mann-Whitney U test relative to the independent t-test. It can be proven that the ARE (or Pitman efficiency) is never less than 86.4%. When the sample size is increased by 15%, the equivalent power should be achieved, since 1.15 is approximately 1/0.864.
- b. The sample size will be increased to a total of 43 subjects per group to allow for the prediction that approximately 5% of cochlear implant recipients will not exhibit an intraoperative CM response (Dalbert et al. 2015).

## **3.2 Analyses**

### **3.2.1 Pass/Fail Criteria**

Not Applicable

The null and alternative hypotheses are as follows:

$$H_0: CM^- - CM^+ \leq 0$$

$$H_a: CM^- - CM^+ > 0$$

where:

$CM^-$  = mean or median drop in low frequency postoperative hearing at 4-6 weeks post-activation (FUV1) for the compromised CM group.

$CM^+$  = mean or median drop in low frequency postoperative hearing at 4-6 weeks post-activation (FUV1) for the preserved CM group.

If additional multiple regression analyses specified in 3.4.4 indicate the presence of covariates explaining a significant amount of variance in acoustic hearing preservation, the primary endpoint will also be tested using a general linear model (ANCOVA) that controls for the influence of covariates. If there is significant departure of the difference in hearing thresholds from normality, the data used in the ANCOVA will be transformed to better approximate normality.

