2 SYNOPSIS

Investigation title	Association between Intra-Operative Cochlear Response Telemetry and Hearing Preservation (CREST)
Investigation number	CLTD 5667
Name of investigational device	Cochlear Response Telemetry (CRT): a system comprising both hardware and software for monitoring the electrophysiological cochlear response to acoustic clicks or short tone bursts. The CRT system is not approved by regulatory agencies.
Investigation start	March 2017
Total expected duration of the clinical investigation	17 months
Enrolment period	12 months
Expected duration per subject	5 months
Investigational design	
Prospective, multi-center, observational (non-randomized) investigation consisting of a pre-operative visit and treatment visits at the time of implantation (Day 0), at 4-6 weeks post-surgery follow-up visit (FUV1) and at 3 months post-activation follow-up visit (FUV2). Subjects will be allocated into two groups according to their residual hearing at FUV1.
 
Visit Schedule:
 
Pre-Operative Visit POV1 (up to 90 days before D0) Intra-Operative Visit D0 Follow-Up Visit 1 FUV1 (4-6 weeks post-surgery +/- 1 week) Follow-Up Visit 2 FUV2 (3M post-activation +/- 2 weeks)

Number of subjects	
Globally: Minimum 86 (Up to 125 depending on monitoring of accruing data affecting proportion of subjects allocated to each group)
 
US: Up to 50; Europe: Up to 40; Australia: Up to 35.

Inclusion criteria	
 • Candidate for cochlear implantation (with CI522, CI532 or Hybrid-L24 according to local indications) • 18 years of age or older at the time of enrolment • Pre-operative audiometric threshold in the implanted ear at 500 Hz of better than or equal to 80 dB HL • Willingness to participate in and to comply with all requirements of the protocol

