**Investigation Schedule**

Procedure	POV1 Pre-operative	D0 Surgery	FUV1 4-6 Weeks Post-Surgery (+/- 1 week)	FUV2 3-Month Post-Activation (+/- 2 weeks)
Medical and Hearing History	X			
Otoscopy (Check for Wax Occlusion)	X	X	X	X
Cochlear Response Telemetry (CRT)		X	X (either FUV1 or FUV2)	
Audiometry & Tympanometry	X		X	X
Surgical Questionnaire		X		
Impedance Measures (Standard, 4-point, Voltogram)		X	X (either FUV1 or FUV2)	
Optional (where obtained at sites as part of routine clinical management): Imaging (MRI Pre-Operative; X-Ray or Cone Beam CT Post-Operative)	X		X	

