To facilitate ease of measurement of the ECoG responses, the University of Melbourne in collaboration with Cochlear Limited have developed a prototype software and hardware system (termed Cochlear Response Telemetry, CRT). The system utilizes the in-built cochlear implant amplifier of the implant receiver-stimulator to record the evoked responses to acoustic stimuli from intra-cochlear electrodes. Recent research at the University of Melbourne and Royal Victorian Eye and Ear Hospital Cochlear Implant Clinic (Campbell et al. 2016) has demonstrated 15dB better low frequency hearing preservation in patients with preserved CM responses during surgery than in those where the CM was shown to reduce in amplitude during the surgical procedure without recovery. Furthermore, the preliminary findings from that study suggest that the real-time monitoring of the CM might in the future inform optimal electrode placement and identify events in surgery that might be detrimental to ensuring acoustic hearing preservation.

The present investigation primarily aims to confirm the Campbell et al. 2016 finding of better low frequency hearing preservation with preserved intra-operative CM responses in a much larger group of cochlear implant recipients across different centers. Hearing preservation will be investigated at 4-6 weeks and 3 months post-implantation. Of primary interest will be the hearing preservation at 4-6 weeks post-implantation, which is less likely to be impacted by factors other than potentially traumatic surgical events. In contrast to the Campbell et al. (2016) study, this study's categorization of hearing preservation will not include 250 Hz. This acoustic frequency is less likely to be sensitive to the CM measurement, since the hair cell population for 250 Hz lies deeper than the typical electrode array insertion. In the present study, acoustic hearing deterioration will be measured across a range of

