Implant surgery will be conducted (at D0). A video recording will be made during the surgical procedure to enable analysis of the CRT in response to specific surgical events. The video will be made via the operative microscope imaging system during the entire insertion, commencing just prior to cochlear opening and ending after closure of the deep (subcutaneous/muscle) layer. The video will be time-stamped to the CRT recordings. Measures of electrode impedance will be obtained during the surgery. At the completion of each subject's surgical procedure a questionnaire will be completed by the surgeon to document aspects of the surgical procedure (including surgical approach, administration of corticosteroids, and ease and depth of electrode insertion).

Post-operative assessment at 4-6 weeks (+/- 1 week) post-activation and 3 months (+/- 2 weeks) post-activation will be conducted, and involve a series of clinical tests including otoscopy, audiometry, tympanometry and electrode impedance assessment. At either 4-6 weeks post-surgery (+/- 1 week), or 3 months (+/- 2 weeks) post-activation, post-operative CRT will also be conducted.

If an intra-or post-operative imaging is performed as part of the routine clinical management at participating site, that data will be analyzed to provide an estimate of electrode array position.

Medical and audiological care throughout the clinical investigation, and at the conclusion of the investigation, will be as per standard clinical protocol for each investigational site, with the exception of the additional measurements taken as outlined.

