8 STATISTICAL CONSIDERATIONS

The primary hypothesis will be tested with a between-groups t-test or non-parametric Mann-Whitney U test using a one-sided alpha level of 0.05. This analysis will compare group mean low frequency postoperative hearing deterioration at FUV1 in the implanted ear for subjects with compromised CM compared to subjects with preserved CM. Compromised CM will be defined as a CM with an irreversible reduction in amplitude during surgery; specifically a $\geq 30\%$ reduction in maximum CM amplitude that does not recover to within 10% of the maximum amplitude. Preserved CM will be defined as a CM with $< 30\%$ amplitude reduction at any point during the surgery. Subjects not falling into the compromised or preserved CM groups will not be included in the analysis. The mean or median threshold drop for the CM compromised and CM preserved groups will be separately calculated as the mean or median of individual subjects' low frequency deterioration (4-6 week post-surgery threshold minus pre-operative threshold in the implanted ear) for the corresponding CM group. For each subject, the low frequency deterioration will be calculated as the average deterioration across the frequencies 500 Hz, 750 Hz and 1000 Hz, where there is preoperative hearing better than or equal to 80 dB HL in the implanted ear. For example, if a subject's preoperative hearing threshold is better than or equal to 80 dB HL at 500 Hz and 750 Hz but is 90 dB HL at 1 kHz, the hearing deterioration (post-operative threshold minus preoperative threshold) will be computed at 500 Hz and 750 Hz only and then averaged. It is possible that a subject could have hearing deterioration measured at 500 Hz only, if preoperative thresholds at 750 Hz and 1 kHz exceed 80 dB HL. Non-measurable post-operative thresholds will be assigned a value 1 dB above the level at which the limits of the audiometer were reached. Vibrotactile responses will not be included in the analyses.

Sample Size Estimation

Prospective sample size estimation for a two-sample t-test has been conducted, given that the study uses a between-groups design to investigate its primary hypothesis. Specifically, the planned sample size would provide 80% power at the one-tailed 0.05 alpha level to detect at least 15 dB greater deterioration in low frequency acoustic hearing threshold for subjects with compromised CM compared to preserved CM.

The following general assumptions have been made:

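### The primary outcome's time point is stated three ways: 4-6 weeks after surgery, 4-6 weeks after activation, and 3 months after activation

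*SAP*

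**What the plan says.** **Counted from surgery.** The synopsis visit schedule (Protocol 2) gives "Follow-Up Visit 1 FUV1 (4-6 weeks post-surgery +/- 1 week", and the column heading in the Investigation Schedule is "4-6 Weeks Post-Surgery (+/- 1 week". Protocol 8 calculates each subject's deterioration as the "4-6 week post-surgery threshold minus pre-operative threshold in the implanted ear". Protocol 4 gives the reason for the choice: primary interest is in "hearing preservation at 4-6 weeks post-implantation, which is less likely to be impacted by factors other than potentially traumatic surgical events".

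**Counted from activation.** Protocol 7.2 states: "Post-operative assessment at 4-6 weeks (+/- 1 week) post-activation and 3 months (+/- 2 weeks) post-activation will be conducted". That sentence goes on to list audiometry among the tests. SAP 3.2.2 defines CM- as the "mean or median drop in low frequency postoperative hearing at 4-6 weeks post-activation (FUV1) for the compromised CM group", and CM+ in the same way for the preserved group.

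**Both anchors together.** The next sentence of Protocol 7.2 returns to surgery for the early visit: "At either 4-6 weeks post-surgery (+/- 1 week), or 3 months (+/- 2 weeks) post-activation, post-operative CRT will also be conducted".

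**A third time point.** SAP 3.2.2 opens by naming FUV1. Its calculation text then subtracts the pre-operative threshold from the threshold at 3 months post-activation, which is the FUV2 time point in the synopsis and the schedule.

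**FUV2.** The synopsis, the schedule, Protocol 7.2 and SAP 3.2.3 count it from activation. Protocol 4 twice places the 3-month assessment after implantation.

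The Protocol 21 change history says that version 3.0 (August 2017) clarified the FUV1 and FUV2 windows. SAP V3 is later (May 2019).

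**The concern.** The time point is part of the definition of the primary outcome. Protocol 4 chose the early visit because it should reflect surgical trauma more than anything else, so time since surgery is the quantity that matters. Activation is not a visit in the schedule and no passage gives its day. A site that books FUV1 by the assessment sentence in Protocol 7.2 would therefore measure later than one that follows the schedule, by an interval the plan does not control.

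Nothing later in the plan would show this. The per-protocol set in SAP 3.3.2 asks only for hearing and CM data and has no timing condition. The covariates named in SAP 3.4.4 are age, gender and intra-operative steroids.

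The 3-month wording is a separate problem, because it points the analyst to a different visit's data. SAP 3.2.3 says that the first secondary hypothesis follows the same analysis considerations as the primary. Taken literally, the primary calculation would then be the FUV2 comparison of secondary hypothesis 1.

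**Working it through.** **The plan's own figure.** Inputs from Protocol 8 and SAP 3.1: difference 15 dB, SD 25 dB, one-sided alpha 0.05, power 0.80. The normal approximation is n = 2 × (1.645 + 0.842)² × (25/15)² = 34.4, or 35 per group. The noncentral-t calculation gives 35.04, rounded up to 36, with power 0.809 at 36. The stated 36 per group is reproduced. Visit timing does not enter the formula, so this figure does not change.

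**FUV1 windows.** Let L be the weeks from surgery to activation. The documents do not give L, so the values below are assumptions.

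- Counted from surgery: 4-6 ± 1, or weeks 3 to 7 after surgery.
- Counted from activation: weeks 3+L to 7+L after surgery.
- Overlap with tolerance: max(0, 4 − L) weeks. Overlap of the nominal 4-6 week windows: max(0, 2 − L) weeks.

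| L (weeks, assumed) | From surgery | From activation | Overlap with tolerance | Nominal windows |
|---|---|---|---|---|
| 1 | 3-7 | 4-8 | 3 weeks | 4-6 and 5-7, overlap 1 week |
| 2 | 3-7 | 5-9 | 2 weeks | 4-6 and 6-8, touch |
| 3 | 3-7 | 6-10 | 1 week | 4-6 and 7-9, disjoint |
| 4 | 3-7 | 7-11 | touch at week 7 | 4-6 and 8-10, disjoint |
| 5 | 3-7 | 8-12 | none, 1-week gap | 4-6 and 9-11, disjoint |

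**Do the documents bound L?** Only indirectly. The synopsis expects 5 months per subject. Five months is 21.74 weeks and three months is 13.04 weeks, which leaves 21.74 − 13.04 = 8.70 weeks before activation. If the 5 months include the pre-operative wait, L is shorter. An L above 4 is not excluded, and neither is an L of 1.

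**The 3-month wording.** Three months ± 2 weeks after activation is 13.04 ± 2 = 11.04 to 15.04 weeks, plus L, after surgery. Its earliest point (11.04, at L = 0) is later than week 7, so it never overlaps the surgery-anchored FUV1 window.

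**Distance between FUV1 and FUV2.** If both count from activation, FUV1 closes at week 7 and FUV2 opens at 11.04 weeks, a gap of about 4 weeks. If FUV1 counts from surgery, the gap is about 4 + L weeks.

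**The case against.** The best defence is that the intended anchor is clear. The synopsis, the schedule table, Protocol 8 and the CRT sentence of 7.2 all say surgery, and the Protocol 4 rationale says implantation. Nothing ranks the one assessment sentence in 7.2 above the schedule, so many sites may have used surgery throughout. This stands as a reason why the damage may be small. It does not make the SAP's definition of the tested quantity correct.

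A reader might infer four stronger things that the documents do not support:

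- **That the two FUV1 windows do not overlap.** With tolerance, this needs L above 4 weeks, and L is not stated.
- **That counting from surgery gives an audiogram before electrical stimulation and counting from activation does not.** For L of 3 weeks or less, the whole of weeks 3-7 is also at or after activation. Neither anchor guarantees a pre-stimulation audiogram.
- **That analysts could pick different weeks.** Each subject has one scheduled FUV1 audiogram and the SAP names that visit, so the surgery/activation wording offers no second dataset. Only the 3-month wording does.
- **That the comparison of CM groups is biased.** Timing differences between sites would bias it only if they also went with CM group. Nothing in the documents shows this, and surgeons receive no CM feedback during insertion (Protocol 7.3.3).

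FUV1 and FUV2 also remain distinct visits under either anchor. The FUV2 discrepancy is loose wording in the rationale section, since the operative passages agree.

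**Conclusion.** The inconsistency is real and stands in the current text of both documents. SAP 3.2.2 alone gives two time points for the primary outcome, 4-6 weeks and 3 months after activation, and neither matches the calculation in Protocol 8.

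A site following the assessment sentence in Protocol 7.2 would take the primary audiogram L weeks later than one following the schedule. The shift exists for any L above 0, but its size is unknown because L is an assumption throughout. The 3-month wording describes a different visit whatever the value of L.

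No effect in dB and no bias between CM groups can be derived from the documents. Sample size, alpha and power are untouched. The point rests on the definition of the primary outcome, which should be unambiguous before the analysis is run.

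**What to change.** 1. **Use one FUV1 time point.** Reconcile the assessment sentence in Protocol 7.2, the CM- and CM+ definitions in SAP 3.2.2 and the 3-month calculation text in SAP 3.2.2 with the synopsis, the Investigation Schedule, the Protocol 4 rationale and the Protocol 8 calculation. Changing the CM-/CM+ definitions alone would leave the primary calculation at the FUV2 time point.
2. **Align FUV2.** Bring the two mentions in Protocol 4 into line with the synopsis and the schedule.
3. **Show the timing.** In the SAP, derive days from surgery to FUV1 audiometry and report the distribution by CM group.
4. **Add a sensitivity analysis.** Keep all FUV1 audiograms in the primary analysis, and repeat it on those inside the stated window. The wording conflict does not require excluding out-of-window audiograms from the primary set, and doing so would cost subjects.

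The cost is a few sentences, one derived variable that needs only the surgery and audiogram dates, and one extra run of the same test. Corrected protocol wording helps only visits still to come. For visits already made, the derived variable shows what happened.
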